6.10.2 Adverse Events

All AEs that occur during the study will be recorded and classified on the basis of Medical Dictionary for Regulatory Activities (MedDRA) terminology. Treatment-emergent AEs (TEAEs) are defined as AEs with an onset on or after the date of the first study drug application. Adverse events noted prior to the first study drug administration that worsen after Baseline will also be reported as AEs and included in the summaries.

An overall summary of TEAEs will be presented showing the number of subjects reporting at least one TEAE, number reporting at least one SAE, number reporting at least one TEAE leading to study discontinuation, and number of TEAEs by severity and by relationship for each treatment group. The total number of AEs will also be presented as part of the overall summary of TEAEs. Treatment-emergent AEs will be summarized by system organ class and preferred name. Serious TEAEs, Related TEAEs, Severe TEAEs, and TEAEs leading to study discontinuation will also be summarized by system organ class and preferred name.

In addition, a listing of all AEs, a listing of Serious AEs, and a listing of subjects who prematurely discontinued from the study due to an AE will be provided.

No statistical inference between treatments will be performed on AEs.

6.10.2.1 Drug Abuse and Liability Assessments

Adverse events associated with potential abuse or overdose will be recorded and classified by MedDRA System Organ Classifications (SOC) and MedDRA Preferred Terms (PTs) as outlined in the Safety Management Plan. The incidence of abuse related AEs will be summarized by treatment group using frequency counts and percentages.

A by-subject listing of abuse related AEs will also be presented.

6.10.3 Clinical Laboratory Evaluation

Laboratory test results will be summarized with descriptive statistics at Baseline and Day 84. Additionally, shifts from Baseline to Day 84 in laboratory test results based on normal ranges will be summarized with frequency counts and percentages. Individual laboratory test results as well as pregnancy test results will be presented in a by-subject listing.

6.10.4 Other Observations Related to Safety

6.10.4.1 Cutaneous Tolerability Assessments

Cutaneous tolerability (erythema, scaling, dryness, pruritus, and burning/stinging) will be summarized at each visit using counts and percentages by treatment group. In addition, worst post-Baseline grade will be summarized by treatment group using counts and percentages. Any incident of mild, moderate, or severe post-Baseline results will be summarized by treatment group using counts and percentages.

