mg/kg/day (225 mg CBD/day or 0.398 mg/cm²/day) applied as 3 mL of BTX 1503 5% (w/w) BID for 28 days was shown to be safe and well-tolerated. There was only 1 AE associated with the study drug treatment; application site pain (sore eyes). Slight to moderate erythema was reported most frequently in cutaneous tolerability assessments. However, most subjects that reported erythema pre or post-study drug application had erythema at Baseline and treatment with BTX 1503 did not exacerbate the erythema. Only 1 subject had increased erythema from Baseline and this was reported at Day 35, seven days after their final application of study drug. Slight scaling was reported in 2 subjects (9.5%), slight dryness was reported in 4 subjects (19.0%) and slight burning/stinging was reported in 5 subjects (23.4%). Only 1 positive cutaneous tolerability assessment (slight dryness) was reported at more than a single visit.

In support of this planned Phase 2 clinical study, dermal toxicology studies of 90 days in duration in minipigs with BTX 1503 have not revealed any clinically significant toxicities or laboratory abnormalities. Details on the results of these studies are provided in the Investigator's Brochure.

The published literature has suggested that CBD may be an inhibitor of human cytochrome P450 CYP1A1 at concentrations that are 9.7-fold of observed maximum plasma concentrations (C_{max}) in clinical studies with BTX 1503.

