9.4.2. Safety Analyses

All subjects who receive at least one confirmed dose of study drug and have at least one post-Baseline assessment will be included in the safety analyses.

All treatment-emergent adverse events (TEAEs) reported during the study will be recorded and classified based on MedDRA terminology. Treatment-emergent adverse events are those AEs with an onset on or after the first application of study medication. All reported TEAEs will be summarized by treatment group, the number of subjects reporting events, system organ class, preferred term, severity, relationship to study drug, and seriousness. When summarizing events by causality and severity, each subject will be counted only once within a system organ class or a preferred term by using the event with the greatest relationship and highest severity within each classification.

Serious adverse events (SAEs) will be summarized by cohort, system organ class, preferred term, severity, outcome and relationship to study drug; and all SAEs will be listed by subject. In addition, a list of subjects who prematurely discontinue from the study due to an AE and the reason for discontinuation will be provided.

Concomitant medication will be mapped to ATC Level 2 using the WHODrug dictionary. The number and percentage of subjects reporting each medication will be summarized. Medications taken by each subject will be listed.

Changes from Baseline in safety laboratory assessments (CBC, chemistry and urinalysis) at Day 84 will be summarized using shift tables. Abnormal values will be summarized. Laboratory values will be listed by subject.

Cutaneous tolerability will be assessed at the Baseline, Day 14, Day 28, Day 56 and Day 84 Visits. Summaries will present frequencies and percentages for the grading of each of the signs/symptoms that was performed at each scheduled visit/time point combination. The summary of cutaneous tolerability assessment scores table will present summary statistics for the scores ('None'=0, 'Slight'=1, 'Moderate'=2 and 'Severe'=3) and the change from Baseline values at each scheduled post-Baseline visits/time point for each of the signs/symptoms. Listings will be provided by subject.

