8. CHANGES IN THE PLANNED ANALYSES

There are no changes in the conduct of the study or planned analyses.

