Moderate	xx (xx.x%)	xx (xx.x%)	xx (xx.x%)	xx (xx.x%)	xx (xx.x%)	xx (xx.x%)	xx (xx.x%)
Mild	xx (xx.x%)	xx (xx.x%)	xx (xx.x%)	xx (xx.x%)	xx (xx.x%)	xx (xx.x%)	xx (xx.x%)
None	xx (xx.x%)	xx (xx.x%)	xx (xx.x%)	xx (xx.x%)	xx (xx.x%)	xx (xx.x%)	xx (xx.x%)

[Repeat for Dryness and Scaling]

Note: Percentages are based on the number of subjects in each treatment group in the Safety population with at least one post-baseline assessment for the given category.

SOURCE: USERNAME\SPONSOR\PROJECT\JOBNAME (DATE,TIME)

Table 14.3.0.2.3: Summary of Mild, Moderate, or Severe Post-Baseline Cutaneous Tolerability Assessments
(Safety Population)
(Page x of y)

	Vehicle QD (N=xx)	Vehicle BID (N=xx)	Vehicle Combined (N=xx)	BTX 1503 5% BID (N=xx)	BTX 1503 5% QD (N=xx)	BTX 1503 2.5% QD (N=xx)	BTX 1503 Combined (N=xx)
Post-Baseline							
n	xx	xx	xx	xx	xx	xx	xx
Burning/Stinging	xx (xx.x%)	xx (xx.x%)	xx (xx.x%)	xx (xx.x%)	xx (xx.x%)	xx (xx.x%)	xx (xx.x%)
Pruritus	xx (xx.x%)	xx (xx.x%)	xx (xx.x%)	xx (xx.x%)	xx (xx.x%)	xx (xx.x%)	xx (xx.x%)
Erythema	xx (xx.x%)	xx (xx.x%)	xx (xx.x%)	xx (xx.x%)	xx (xx.x%)	xx (xx.x%)	xx (xx.x%)
Dryness	xx (xx.x%)	xx (xx.x%)	xx (xx.x%)	xx (xx.x%)	xx (xx.x%)	xx (xx.x%)	xx (xx.x%)
Scaling	xx (xx.x%)	xx (xx.x%)	xx (xx.x%)	xx (xx.x%)	xx (xx.x%)	xx (xx.x%)	xx (xx.x%)

Note: Percentages are based on the number of subjects in each treatment group in the Safety population with at least one post-baseline assessment.

SOURCE: USERNAME\SPONSOR\PROJECT\JOBNAME (DATE,TIME)

Table 14.3.1.1: Summary of Treatment-Emergent Adverse Event Characteristics
 (Safety Population)

	Vehicle QD (N=xx)	Vehicle BID (N=xx)	Vehicle Combined (N=xx)	BTX 1503 5% BID (N=xx)	BTX 1503 5% QD (N=xx)	BTX 1503 2.5% QD (N=xx)	BTX 1503 Combined (N=xx)
Number (%) of Subjects Reporting At Least One Treatment-Emergent Adverse Event	xx (xx.x%)	xx (xx.x%)	xx (xx.x%)	xx (xx.x%)	xx (xx.x%)	xx (xx.x%)	xx (xx.x%)
Number of Treatment-Emergent Adverse Events	xx	xx	xx	xx	xx	xx	xx
Number (%) of Subjects Reporting At Least One Serious Treatment-Emergent Adverse Event	xx (xx.x%)	xx (xx.x%)	xx (xx.x%)	xx (xx.x%)	xx (xx.x%)	xx (xx.x%)	xx (xx.x%)
Number of Serious Treatment-Emergent Adverse Events	xx	xx	xx	xx	xx	xx	xx
Number (%) of Subjects who Discontinued Study Due to At Least One Treatment-Emergent Event	xx (xx.x%)	xx (xx.x%)	xx (xx.x%)	xx (xx.x%)	xx (xx.x%)	xx (xx.x%)	xx (xx.x%)
Number of Treatment-Emergent Adverse Events Leading to Discontinuation of Study	xx	xx	xx	xx	xx	xx	xx
Maximum Severity							

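### The SAP drops the protocol's change-from-Baseline tolerability summary without declaring it, and its worst-grade and any-incident tables count signs already present at Baseline, which can dilute the contrast between arms

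*SAP*

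**What the plan says.** Protocol 9.4.2 plans two tolerability displays. One gives grade frequencies at each visit and time point. The other gives summary statistics for the 0–3 scores "and the change from Baseline values at each scheduled post-Baseline visits/time point for each of the signs/symptoms".

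SAP 6.10.4.1 plans three displays:

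- By visit (Table 14.3.0.2.1): the five signs and symptoms "will be summarized at each visit using counts and percentages by treatment group".
- Worst grade (Table 14.3.0.2.2): "worst post-Baseline grade will be summarized by treatment group using counts and percentages".
- Any incident (Table 14.3.0.2.3): "Any incident of mild, moderate, or severe post-Baseline results will be summarized by treatment group using counts and percentages".

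The shells for these tables have no score statistics, no change-from-Baseline rows and no tolerability shift table. The note under the any-incident shell sets the denominator: "Percentages are based on the number of subjects in each treatment group in the Safety population with at least one post-baseline assessment". SAP section 8 states: "There are no changes in the conduct of the study or planned analyses".

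On Baseline signs, Protocol 2.2.2 reports from the 21-subject Phase 1b study that "most subjects that reported erythema pre or post-study drug application had erythema at Baseline".

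**The concern.** A summary specified in the protocol has disappeared between protocol and SAP, and the section meant to record such changes says there are none.

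What replaces it is not tied to the subject's own starting grade. Someone with mild erythema before dosing who stays mild enters the any-incident table as a post-Baseline finding. In that table the subject looks the same as someone who went from mild to moderate. In the worst-grade table, someone moderate throughout looks the same as someone who went from none to moderate.

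This is a vehicle-controlled dose-finding study, and Protocol 2.3 names tolerability among the things it is designed to investigate. What a reader needs to know is whether the drug adds irritation to what was already there. The protocol's own reading of Phase 1b, that treatment did not exacerbate erythema, rests on a within-subject comparison: one subject rose above Baseline. No table planned in the SAP would yield that count.

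**Working it through.** **Comparison of the documents (no assumptions needed)**

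- Score statistics by time point: in Protocol 9.4.2; absent from SAP 6.10.4.1 and its shells.
- Change from Baseline by time point: in Protocol 9.4.2; absent from SAP 6.10.4.1 and its shells.
- Declared in SAP section 8: no.
- Baseline-to-Day-84 shifts: planned for laboratory tests (SAP 6.10.3), not for tolerability.

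**When counting starts.** SAP 6.1.2 takes Baseline as the last value before first application. Protocol Table 3 schedules a rating about 15 minutes after the first dose, and the by-visit shell carries that time point. It is therefore post-Baseline, and the SAP does not exclude it from the worst-grade or any-incident tables. Pruritus and burning/stinging are rated over the preceding 24 hours (Protocol 7.1), so that rating mostly describes the time before dosing.

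**Size of the dilution.** The documents give no figure to reproduce, so this is an illustration. Let

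- b = proportion with the sign at Baseline (not given; taken as 20% to 80%),
- w = true rate of worsening above Baseline (not given; taken as 5% on vehicle and 20% on active, the same with or without the sign at Baseline),
- s = proportion of Baseline-positive subjects still positive at some post-Baseline rating (not given; taken as 100%, then 90%).

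P(any incident) = b[s + (1 − s)w] + (1 − b)w.

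The coefficient of w is b(1 − s) + (1 − b) = 1 − sb. The difference shown between arms is therefore (1 − sb) times the true difference. With s = 1 the factor is 1 − b.

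Results with s = 1 and a true difference of 20 − 5 = 15 points:

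| b | Vehicle | Active | Difference shown | Active-arm incidents without worsening |
|---|---|---|---|---|
| 20% | 0.20 + 0.80×0.05 = 24% | 0.20 + 0.80×0.20 = 36% | 12 points | 1 − 20/36 = 44% |
| 40% | 0.40 + 0.60×0.05 = 43% | 0.40 + 0.60×0.20 = 52% | 9 points | 1 − 20/52 = 62% |
| 60% | 0.60 + 0.40×0.05 = 62% | 0.60 + 0.40×0.20 = 68% | 6 points | 1 − 20/68 = 71% |
| 80% | 0.80 + 0.20×0.05 = 81% | 0.80 + 0.20×0.20 = 84% | 3 points | 1 − 20/84 = 76% |

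Varying the assumptions:

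- s = 0.9: 15 × (1 − 0.9b) = 12.3, 9.6, 6.9 and 4.2 points.
- Worsening of 10% versus 20%, s = 1: 10 × (1 − b) = 8, 6, 4 and 2 points against a true 10.

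A count of subjects who rise above Baseline would show the full 15 (or 10) points at every prevalence, because it measures w directly.

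**The case against.** The strongest reply is that the three tables should be read together.

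- The by-visit table opens with a Baseline row, so a net shift in an arm's grade distribution can be seen for each sign.
- The worst-grade table separates mild from moderate, so the any-incident table is the least informative of the three.
- Listing 16.2.7.1 gives every subject's grade by visit and time point.
- Worsening may also reach the adverse event tables, since SAP 6.10.2 includes events that worsen after Baseline.

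All of this stands, so the masking is partial. It does not replace a within-subject display. Marginal percentages cannot show who worsened. The worst-grade table still mixes stable-moderate with newly moderate subjects. The adverse event route depends on the investigator recording a change in a sign as an event. A derivation from the listing after the fact is weaker than a specified table.

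It can also be said that the synopsis describes the tolerability summary without change from Baseline, and that the protocol never planned a shift table. Both are true. The synopsis is silent rather than contradictory, and 9.4.2 is explicit. The shift table is an addition worth making: mean change on a 0–3 scale nets improvement against worsening, so restoring it alone would not show who worsened.

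A reader might also infer more than the documents support:

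- *That the trial loses power to detect irritation.* No tolerability hypothesis, alpha level or test is planned; the displays are counts and percentages. Power figures do not apply.
- *That tolerability is the formal objective or the basis for 360 subjects.* The objective in both documents is safety and efficacy. The sample size rests on clinical considerations and is only judged adequate for safety and tolerability.
- *That Baseline signs are known to be frequent across all five items.* The Phase 1b statement concerns erythema only. It describes a share of those who had erythema, not a prevalence.

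**Conclusion.** The point holds as an undeclared departure from the protocol, with a reporting weakness attached. The departure is a matter of text and needs no assumption.

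The weakness is that two of the three planned tables count signs regardless of Baseline grade. This raises the rate within each arm and can shrink the any-incident difference between arms by the factor (1 − Baseline prevalence) if Baseline signs persist. The actual size cannot be known from the documents. The 12, 9, 6 and 3 points shown for a true 15 depend on the assumed 5% and 20% worsening, equal worsening with and without the sign at Baseline, and full persistence; at 90% persistence the loss is somewhat smaller. If Baseline prevalence is low for a sign, its dilution is slight.

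The documents do not support saying that the tables hide irritation altogether. The right description is partial dilution, most plausible for erythema.

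**What to change.** Amend SAP 6.10.4.1 and the shells before unblinding:

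1. Restore the score and change-from-Baseline summary by visit and time point, as in Protocol 9.4.2. If it is to be left out on purpose, say so in SAP section 8 and give the reason.
2. Add, per sign and arm, the number and percentage of subjects with any post-Baseline grade above the pre-dose Day 1 grade.
3. Add, per sign and arm, a shift table of Baseline grade by worst post-Baseline grade.
4. Keep the three existing tables as supporting displays.

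The only cost is a few more tables. All the data are already collected under the protocol's schedule, and no visit, procedure or sample size changes.

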6.10.4.2 Physical Examination

Physical examination data will be presented in a by-subject listing.

7. DETERMINATION OF SAMPLE SIZE

The sample size for this study is based on clinical considerations only. Subjects will be randomized 2:2:2:1:1 with 90 subjects in each active treatment group and 45 subjects in each vehicle group for a total 360 subjects. This is considered adequate to evaluate the safety and tolerability of BTX 1503 in the treatment of acne vulgaris.

8. CHANGES IN THE PLANNED ANALYSES

There are no changes in the conduct of the study or planned analyses.

Table 14.3.1.1.3: Summary of Serious Treatment-Emergent Adverse Events by MedDRA System Organ Class and Preferred Term (Safety Population).....	150
Table 14.3.1.1.4: Summary of Related Treatment-Emergent Adverse Events by MedDRA System Organ Class and Preferred Term (Safety Population).....	150
Table 14.3.1.1.5: Summary of Severe Treatment-Emergent Adverse Events by MedDRA System Organ Class and Preferred Term (Safety Population).....	150
Table 14.3.1.1.6: Summary of Treatment-Emergent Adverse Events Leading to Study Discontinuation by MedDRA System Organ Class and Preferred Term (Safety Population).....	150
Table 14.3.1.1.7: Summary of Treatment-Emergent Abuse-Related Adverse Events by MedDRA System Organ Class and Preferred Term (Safety Population).....	150
Table 14.3.1.2.1.1: Summary of Chemistry Results by Visit (Safety Population).....	151
Table 14.3.1.2.1.2: Shift Table for Chemistry Results (Safety Population).....	152
Table 14.3.1.2.2.1: Summary of CBC Results by Visit (Safety Population).....	154
Table 14.3.1.2.2.2: Shift Table for CBC Results (Safety Population).....	154
Table 14.3.1.2.3.1: Summary of Numeric Urinalysis Results by Visit (Safety Population).....	154
Table 14.3.1.2.3.2: Shift Table for Numeric Urinalysis Results (Safety Population).....	154
Table 14.3.1.2.3.3: Summary of Character Urinalysis Results by Visit (Safety Population).....	155

Table 14.0.1: Summary of Subject Completion/Discontinuation
 (Randomized Subjects)

	Vehicle QD (N=xx)	Vehicle BID (N=xx)	Vehicle Combined (N=xx)	BTX 1503 5% BID (N=xx)	BTX 1503 5% QD (N=xx)	BTX 1503 2.5% QD (N=xx)	BTX 1503 Combined (N=xx)
Completed Study							
Yes	xx (xx.x%)	xx (xx.x%)	xx (xx.x%)	xx (xx.x%)	xx (xx.x%)	xx (xx.x%)	xx (xx.x%)
No	xx (xx.x%)	xx (xx.x%)	xx (xx.x%)	xx (xx.x%)	xx (xx.x%)	xx (xx.x%)	xx (xx.x%)
Reason for Discontinuation from Study							
Adverse Event	xx (xx.x%)	xx (xx.x%)	xx (xx.x%)	xx (xx.x%)	xx (xx.x%)	xx (xx.x%)	xx (xx.x%)
Death	xx (xx.x%)	xx (xx.x%)	xx (xx.x%)	xx (xx.x%)	xx (xx.x%)	xx (xx.x%)	xx (xx.x%)
Lost to Follow-Up	xx (xx.x%)	xx (xx.x%)	xx (xx.x%)	xx (xx.x%)	xx (xx.x%)	xx (xx.x%)	xx (xx.x%)
Physician Decision	xx (xx.x%)	xx (xx.x%)	xx (xx.x%)	xx (xx.x%)	xx (xx.x%)	xx (xx.x%)	xx (xx.x%)
Pregnancy	xx (xx.x%)	xx (xx.x%)	xx (xx.x%)	xx (xx.x%)	xx (xx.x%)	xx (xx.x%)	xx (xx.x%)
Protocol Violation	xx (xx.x%)	xx (xx.x%)	xx (xx.x%)	xx (xx.x%)	xx (xx.x%)	xx (xx.x%)	xx (xx.x%)
Study Terminated by Sponsor	xx (xx.x%)	xx (xx.x%)	xx (xx.x%)	xx (xx.x%)	xx (xx.x%)	xx (xx.x%)	xx (xx.x%)
Withdrawal by Subject	xx (xx.x%)	xx (xx.x%)	xx (xx.x%)	xx (xx.x%)	xx (xx.x%)	xx (xx.x%)	xx (xx.x%)
Worsening Condition	xx (xx.x%)	xx (xx.x%)	xx (xx.x%)	xx (xx.x%)	xx (xx.x%)	xx (xx.x%)	xx (xx.x%)
Other	xx (xx.x%)	xx (xx.x%)	xx (xx.x%)	xx (xx.x%)	xx (xx.x%)	xx (xx.x%)	xx (xx.x%)

SOURCE: USERNAME/SPONSOR/PROJECT/JOBNAME (DATE,TIME)

Table 14.0.2: Summary of Subjects Excluded from Analyses
 (Randomized Subjects)

	Vehicle QD (N=xx)	Vehicle BID (N=xx)	Vehicle Combined (N=xx)	BTX 1503 5% BID (N=xx)	BTX 1503 5% QD (N=xx)	BTX 1503 2.5% QD (N=xx)	BTX 1503 Combined (N=xx)
Number of Subjects Included in the ITT Population	xx (xx.x%)	xx (xx.x%)	xx (xx.x%)	xx (xx.x%)	xx (xx.x%)	xx (xx.x%)	xx (xx.x%)
Number of Subjects Included in the Safety Population	xx (xx.x%)	xx (xx.x%)	xx (xx.x%)	xx (xx.x%)	xx (xx.x%)	xx (xx.x%)	xx (xx.x%)
Number of Subjects Excluded from the Safety Population	xx (xx.x%)	xx (xx.x%)	xx (xx.x%)	xx (xx.x%)	xx (xx.x%)	xx (xx.x%)	xx (xx.x%)
Reason for Exclusion from the Safety Population							
No Evidence of Subject Dosing	xx (xx.x%)	xx (xx.x%)	xx (xx.x%)	xx (xx.x%)	xx (xx.x%)	xx (xx.x%)	xx (xx.x%)
No Post Baseline Assessment	xx (xx.x%)	xx (xx.x%)	xx (xx.x%)	xx (xx.x%)	xx (xx.x%)	xx (xx.x%)	xx (xx.x%)
Number of Subjects Included in the PP Population	xx (xx.x%)	xx (xx.x%)	xx (xx.x%)	xx (xx.x%)	xx (xx.x%)	xx (xx.x%)	xx (xx.x%)
Number of Subjects Excluded from the PP Population	xx (xx.x%)	xx (xx.x%)	xx (xx.x%)	xx (xx.x%)	xx (xx.x%)	xx (xx.x%)	xx (xx.x%)
Reason for Exclusion from the PP Population							
Violated the Inclusion/Exclusion Criteria	xx (xx.x%)	xx (xx.x%)	xx (xx.x%)	xx (xx.x%)	xx (xx.x%)	xx (xx.x%)	xx (xx.x%)
Received an Interfering Medication	xx (xx.x%)	xx (xx.x%)	xx (xx.x%)	xx (xx.x%)	xx (xx.x%)	xx (xx.x%)	xx (xx.x%)
Has not been Compliant with the Dosing Regimen	xx (xx.x%)	xx (xx.x%)	xx (xx.x%)	xx (xx.x%)	xx (xx.x%)	xx (xx.x%)	xx (xx.x%)
Missed IGA or Lesion Count assessment at Day 84	xx (xx.x%)	xx (xx.x%)	xx (xx.x%)	xx (xx.x%)	xx (xx.x%)	xx (xx.x%)	xx (xx.x%)
Missed Both Day 28 and Day 56 Visits	xx (xx.x%)	xx (xx.x%)	xx (xx.x%)	xx (xx.x%)	xx (xx.x%)	xx (xx.x%)	xx (xx.x%)
Not Compliant with Dosing Regimen	xx (xx.x%)	xx (xx.x%)	xx (xx.x%)	xx (xx.x%)	xx (xx.x%)	xx (xx.x%)	xx (xx.x%)
Day 84 Visit not within +/- 5 days Window	xx (xx.x%)	xx (xx.x%)	xx (xx.x%)	xx (xx.x%)	xx (xx.x%)	xx (xx.x%)	xx (xx.x%)
Other ^a							

^a See Listing 16.2.3 for a complete list of all other reasons for exclusion from the PP population.

Note: ITT exclusion of not being randomized not presented due to requirement of needing to be randomized to be summarized in the table.

Percentages are based on the number of randomized subjects.

SOURCE: USERNAME\SPONSOR\PROJECT\JOBNAME (DATE,TIME)

Table 14.0.3: Summary of Reasons for Screen Failure
(Non-Randomized Subjects)

Reason for Screen Failure	Total (N=xx)
Adverse Event	xx (xx.x%)
Inclusion and/or Exclusion Criteria	xx (xx.x%)
Withdrawal by Subject	xx (xx.x%)
Withdrawal by Legally Authorized Representative	xx (xx.x%)
Lost to Follow-Up	xx (xx.x%)
Other	xx (xx.x%)

Note: Percentages are based on the number of non-randomized subjects.

SOURCE: USERNAME\SPONSOR\PROJECT\JOBNAME (DATE,TIME)

Table 14.1.1.1: Summary of Subject Demographics
 (ITT Population)
 (Page 1 of 2)

	Vehicle QD (N=xx)	Vehicle BID (N=xx)	Vehicle Combined (N=xx)	BTX 1503 5% BID (N=xx)	BTX 1503 5% QD (N=xx)	BTX 1503 2.5% QD (N=xx)	BTX 1503 Combined (N=xx)
Age (years)							
n	xx	xx	xx	xx	xx	xx	xx
Mean	xx.x	xx.x	xx.x	xx.x	xx.x	xx.x	xx.x
SD	xx.xx	xx.xx	xx.xx	xx.xx	xx.xx	xx.xx	xx.xx
Median	xx.x	xx.x	xx.x	xx.x	xx.x	xx.x	xx.x
Min., Max.	xx, xx	xx, xx	xx, xx	xx, xx	xx, xx	xx, xx	xx, xx
Sex							
n	xx	xx	xx	xx	xx	xx	xx
Male	xx (xx.x%)	xx (xx.x%)	xx (xx.x%)	xx (xx.x%)	xx (xx.x%)	xx (xx.x%)	xx (xx.x%)
Female	xx (xx.x%)	xx (xx.x%)	xx (xx.x%)	xx (xx.x%)	xx (xx.x%)	xx (xx.x%)	xx (xx.x%)
Ethnicity							
n	xx	xx	xx	xx	xx	xx	xx
Hispanic or Latino	xx (xx.x%)	xx (xx.x%)	xx (xx.x%)	xx (xx.x%)	xx (xx.x%)	xx (xx.x%)	xx (xx.x%)
Not Hispanic or Latino	xx (xx.x%)	xx (xx.x%)	xx (xx.x%)	xx (xx.x%)	xx (xx.x%)	xx (xx.x%)	xx (xx.x%)

Note: Percentages are based on the number of subjects in the ITT population with a non-missing response.

SOURCE: USERNAME\SPONSOR\PROJECT\JOBNAME (DATE,TIME)

Table 14.1.1.1: Summary of Subject Demographics
(ITT Population)
(Page 2 of 2)

	Vehicle QD (N=xx)	Vehicle BID (N=xx)	Vehicle Combined (N=xx)	BTX 1503 5% BID (N=xx)	BTX 1503 5% QD (N=xx)	BTX 1503 2.5% QD (N=xx)	BTX 1503 Combined (N=xx)
Race							
n	xx	xx	xx	xx	xx	xx	xx
American Indian or Alaska Native	xx (xx.x%)	xx (xx.x%)	xx (xx.x%)	xx (xx.x%)	xx (xx.x%)	xx (xx.x%)	xx (xx.x%)
Asian	xx (xx.x%)	xx (xx.x%)	xx (xx.x%)	xx (xx.x%)	xx (xx.x%)	xx (xx.x%)	xx (xx.x%)
Black or African American	xx (xx.x%)	xx (xx.x%)	xx (xx.x%)	xx (xx.x%)	xx (xx.x%)	xx (xx.x%)	xx (xx.x%)
Native Hawaiian or Other Pacific Islander	xx (xx.x%)	xx (xx.x%)	xx (xx.x%)	xx (xx.x%)	xx (xx.x%)	xx (xx.x%)	xx (xx.x%)
White	xx (xx.x%)	xx (xx.x%)	xx (xx.x%)	xx (xx.x%)	xx (xx.x%)	xx (xx.x%)	xx (xx.x%)
Multiple/Other	xx (xx.x%)	xx (xx.x%)	xx (xx.x%)	xx (xx.x%)	xx (xx.x%)	xx (xx.x%)	xx (xx.x%)

Note: Percentages are based on the number of subjects in the ITT population with a non-missing response.

SOURCE: USERNAME\SPONSOR\PROJECT\JOBNAME (DATE, TIME)

Repeat Table 14.1.1.1 for the following:

Table 14.1.1.2: Summary of Subject Demographics (PP Population)

Table 14.1.1.3: Summary of Subject Demographics (Safety Population)

Table 14.1.2.1: Summary of Baseline Characteristics
(ITT Population)
(Page 1 of 3)

	Vehicle QD (N=xx)	Vehicle BID (N=xx)	Vehicle Combined (N=xx)	BTX 1503 5% BID (N=xx)	BTX 1503 5% QD (N=xx)	BTX 1503 2.5% QD (N=xx)	BTX 1503 Combined (N=xx)
Height (cm)							
n	xx	xx	xx	xx	xx	xx	xx
Mean	xx.x	xx.x	xx.x	xx.x	xx.x	xx.x	xx.x
SD	xx.xx	xx.xx	xx.xx	xx.xx	xx.xx	xx.xx	xx.xx
Median	xx.x	xx.x	xx.x	xx.x	xx.x	xx.x	xx.x
Min., Max.	xx, xx	xx, xx	xx, xx	xx, xx	xx, xx	xx, xx	xx, xx
Weight (kg)							
n	xx	xx	xx	xx	xx	xx	xx
Mean	xx.x	xx.x	xx.x	xx.x	xx.x	xx.x	xx.x
SD	xx.xx	xx.xx	xx.xx	xx.xx	xx.xx	xx.xx	xx.xx
Median	xx.x	xx.x	xx.x	xx.x	xx.x	xx.x	xx.x
Min., Max.	xx, xx	xx, xx	xx, xx	xx, xx	xx, xx	xx, xx	xx, xx
Alcohol History							
n	xx	xx	xx	xx	xx	xx	xx
Drinker	xx (xx.x%)	xx (xx.x%)	xx (xx.x%)	xx (xx.x%)	xx (xx.x%)	xx (xx.x%)	xx (xx.x%)
Non-drinker	xx (xx.x%)	xx (xx.x%)	xx (xx.x%)	xx (xx.x%)	xx (xx.x%)	xx (xx.x%)	xx (xx.x%)
Smoking History							
n	xx	xx	xx	xx	xx	xx	xx
Non-smoker	xx (xx.x%)	xx (xx.x%)	xx (xx.x%)	xx (xx.x%)	xx (xx.x%)	xx (xx.x%)	xx (xx.x%)
Ex-smoker	xx (xx.x%)	xx (xx.x%)	xx (xx.x%)	xx (xx.x%)	xx (xx.x%)	xx (xx.x%)	xx (xx.x%)
Smoker	xx (xx.x%)	xx (xx.x%)	xx (xx.x%)	xx (xx.x%)	xx (xx.x%)	xx (xx.x%)	xx (xx.x%)

SOURCE: USERNAME\SPONSOR\PROJECT\JOBNAME (DATE, TIME)

Table 14.1.2.1: Summary of Baseline Characteristics
(ITT Population)
(Page 2 of 3)

	Vehicle QD (N=xx)	Vehicle BID (N=xx)	Vehicle Combined (N=xx)	BTX 1503 5% BID (N=xx)	BTX 1503 5% QD (N=xx)	BTX 1503 2.5% QD (N=xx)	BTX 1503 Combined (N=xx)
Inflammatory Lesion Count							
n	xx	xx	xx	xx	xx	xx	xx
Mean	xx.x	xx.x	xx.x	xx.x	xx.x	xx.x	xx.x
SD	xx.xx	xx.xx	xx.xx	xx.xx	xx.xx	xx.xx	xx.xx
Median	xx.x	xx.x	xx.x	xx.x	xx.x	xx.x	xx.x
Min., Max.	xx, xx	xx, xx	xx, xx	xx, xx	xx, xx	xx, xx	xx, xx
Non-Inflammatory Lesion Count							
n	xx	xx	xx	xx	xx	xx	xx
Mean	xx.x	xx.x	xx.x	xx.x	xx.x	xx.x	xx.x
SD	xx.xx	xx.xx	xx.xx	xx.xx	xx.xx	xx.xx	xx.xx
Median	xx.x	xx.x	xx.x	xx.x	xx.x	xx.x	xx.x
Min., Max.	xx, xx	xx, xx	xx, xx	xx, xx	xx, xx	xx, xx	xx, xx
Total Lesion Count							
n	xx	xx	xx	xx	xx	xx	xx
Mean	xx.x	xx.x	xx.x	xx.x	xx.x	xx.x	xx.x
SD	xx.xx	xx.xx	xx.xx	xx.xx	xx.xx	xx.xx	xx.xx
Median	xx.x	xx.x	xx.x	xx.x	xx.x	xx.x	xx.x
Min., Max.	xx, xx	xx, xx	xx, xx	xx, xx	xx, xx	xx, xx	xx, xx

SOURCE: USERNAME\SPONSOR\PROJECT\JOBNAME (DATE,TIME)

Table 14.1.2.1: Summary of Baseline Characteristics
(ITT Population)
(Page 3 of 3)

	Vehicle QD (N=xx)	Vehicle BID (N=xx)	Vehicle Combined (N=xx)	BTX 1503 5% BID (N=xx)	BTX 1503 5% QD (N=xx)	BTX 1503 2.5% QD (N=xx)	BTX 1503 Combined (N=xx)
Investigator Global Assessment							
n	xx	xx	xx	xx	xx	xx	xx
Clear	xx (xx.x%)	xx (xx.x%)	xx (xx.x%)	xx (xx.x%)	xx (xx.x%)	xx (xx.x%)	xx (xx.x%)
Almost Clear	xx (xx.x%)	xx (xx.x%)	xx (xx.x%)	xx (xx.x%)	xx (xx.x%)	xx (xx.x%)	xx (xx.x%)
Mild	xx (xx.x%)	xx (xx.x%)	xx (xx.x%)	xx (xx.x%)	xx (xx.x%)	xx (xx.x%)	xx (xx.x%)
Moderate	xx (xx.x%)	xx (xx.x%)	xx (xx.x%)	xx (xx.x%)	xx (xx.x%)	xx (xx.x%)	xx (xx.x%)
Severe	xx (xx.x%)	xx (xx.x%)	xx (xx.x%)	xx (xx.x%)	xx (xx.x%)	xx (xx.x%)	xx (xx.x%)

SOURCE: USERNAME\SPONSOR\PROJECT\JOBNAME (DATE,TIME)

Repeat Table 14.1.2.1 for the following:

Table 14.1.2.2: Summary of Baseline Characteristics (PP Population)

Table 14.1.2.3: Summary of Baseline Characteristics (Safety Population)

Table 14.1.3.1: Summary of Concomitant Medications by ATC Level 2 Term and Preferred Name (ITT Population)

ATC Level 2 Term Preferred Name ^a	Vehicle QD (N=xx)	Vehicle BID (N=xx)	Vehicle Combined (N=xx)	BTX 1503 5% BID (N=xx)	BTX 1503 5% QD (N=xx)	BTX 1503 2.5% QD (N=xx)	BTX 1503 Combined (N=xx)
Subjects with at Least One Concomitant Medication Reported	xx (xx.x%)	xx (xx.x%)	xx (xx.x%)	xx (xx.x%)	xx (xx.x%)	xx (xx.x%)	xx (xx.x%)
ATC Level 2 Term 1	xx (xx.x%)	xx (xx.x%)	xx (xx.x%)	xx (xx.x%)	xx (xx.x%)	xx (xx.x%)	xx (xx.x%)
Preferred Name 1	xx (xx.x%)	xx (xx.x%)	xx (xx.x%)	xx (xx.x%)	xx (xx.x%)	xx (xx.x%)	xx (xx.x%)
Preferred Name 2	xx (xx.x%)	xx (xx.x%)	xx (xx.x%)	xx (xx.x%)	xx (xx.x%)	xx (xx.x%)	xx (xx.x%)
...	xx (xx.x%)	xx (xx.x%)	xx (xx.x%)	xx (xx.x%)	xx (xx.x%)	xx (xx.x%)	xx (xx.x%)
Preferred Name x	xx (xx.x%)	xx (xx.x%)	xx (xx.x%)	xx (xx.x%)	xx (xx.x%)	xx (xx.x%)	xx (xx.x%)
...							

^a WHO-DDE, Format B2, Version MAR 2017.

Note: Concomitant medications are those used on or after the date of first application of study medication.

